9.6.2.1.2 Subjects in 108/110 ES

The analysis for 108/110 ES during 110 Efficacy Analysis Period will be similar to that for 106/110 ES with the exception of different fixed effects: treatment (PBO-TEZ/IVA, IVA-TEZ/IVA, TEZ/IVA), visit, treatment-by-visit interaction and parent study baseline ppFEV₁.

Similarly, the results from this MMRM along with descriptive statistics for observed values and absolute changes from baseline will be presented at scheduled visits within each treatment

group, and LS means ($\pm 95\%$ CI) for absolute change from baseline at each visit will also be plotted by treatment group.

9.6.2.1.3 Subjects in FAS Who Roll Over from Study 103

For FAS patients rolling over from Study 103, descriptive statistics will be summarized for observed values and absolute changes from baseline in ppFEV₁ by treatment group at scheduled visit during 110 Efficacy Analysis Period.

9.6.2.1.4 Subjects in FAS Who Roll Over from Study 111

The analysis for FAS patients rolling over from Study 111 will be similar to that for FAS patients rolling over from Study 103.

9.6.2.2 Number of Pulmonary Exacerbations

9.6.2.2.1 Subjects in 106/110 PEx Analysis Set

The number of PEx during the PEx Analysis Period will be analyzed for 106/110 PEx Analysis Set using a negative binomial regression model and reported as event rate along with the 95% CI. The model will include: treatment (TEZ/IVA, PBO-TEZ/IVA), sex, age group at screening (<18, ≥ 18 years old), and parent study baseline ppFEV₁. The logarithm of PEx analysis period duration will be treated as the offset in this model. If the model does not converge, the negative binomial regression model will be replaced with a Poisson regression model.

Similarly the number of PEx (i) requiring hospitalization, and (ii) requiring IV antibiotic therapy will be analyzed.

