6 STUDY DESIGN

6.1 Overall Design

This is a Phase 3, multicenter, open-label, rollover study in subjects with CF who are homozygous or heterozygous for the *F508del-CFTR* mutation and who participated in Studies VX13-661-103 (Study 103), VX14-661-106 (Study 106), VX14-661-107 (Study 107), VX14-661-108 (Study 108), VX14-661-109 (Study 109), VX14-661-111 (Study 111), Study 112, VX16-661-114 (Study 114), or other Vertex studies investigating VX-661/IVA. The study is designed to evaluate the safety and efficacy of long term treatment of VX-661/IVA.

A schematic of the study design is shown in [Figure 6-1 Study Design](#).

Part A

Part A consists of a Treatment Cohort and an Observational Cohort (see definitions below). Subjects from Studies 103, 106, 107, 108, 109, 111, and other eligible Vertex studies investigating VX-661/IVA, may enroll in Part A. The Treatment Cohort and the Observational Cohort will be open to enrollment in parallel. The analyses specified in this SAP focus on the Part A Treatment Cohort only.

Treatment Cohort

Subjects who completed study drug treatment (i.e., VX-661/IVA, IVA monotherapy, or placebo) during the Treatment Period in the parent study who meet the eligibility criteria (Study Protocol Sections 9.1 and 9.2) will be offered the opportunity to enroll in Study 110. Subjects who permanently discontinue study drug treatment or who withdrew consent during the parent studies are not eligible for enrollment in the Treatment Cohort.

Subjects in the Treatment Cohort will receive VX-661 100 mg/IVA 150-mg fixed-dose combination (FDC) tablet daily (qd) in the morning and IVA 150-mg tablet qd in the evening. The Treatment Period will be approximately 96 weeks.

[figure not shown]

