6.2 Sample Size and Power

Part A

Treatment Cohort

1,044 eligible subjects are enrolled from the following parent studies:

- 23 subjects from Study 103.
- 464 subjects from Study 106.
- 159 subjects from Study 107.

- 227 subjects from Study 108.
- 138 subjects from Study 109.
- 33 subjects from Study 111.

Observational Cohort

No patient enrolled in observational cohort.

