9.6.2.2.2 Subjects in 108/110 PEx Analysis Set

The analysis for 108/110 PEx Analysis Set will be similar to 106/110 PE Analysis Set, with the exception of different fixed effects: treatment (TEZ/IVA, IVA-TEZ/IVA, and PBO-TEZ/IVA), residual function mutation (Class V non-canonical splice and Classes II to IV residual function), age group at screening (<18, ≥ 18 years old), and parent study baseline ppFEV₁.

Similarly the number of PEx (i) requiring hospitalization, and (ii) requiring IV antibiotic therapy will be analyzed.

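### The Poisson fallback for exacerbation counts carries no overdispersion correction, so its 95% CI would be too narrow if the negative binomial fit failed while counts were overdispersed

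*SAP*

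**What the plan says.** SAP 9.6.2.2.1 analyses the number of exacerbations in the 106/110 set "using a negative binomial regression model and reported as event rate along with the 95% CI". Covariates are treatment, sex, age group and parent-study baseline ppFEV₁. On exposure: "The logarithm of PEx analysis period duration will be treated as the offset in this model". The fallback is one sentence: "If the model does not converge, the negative binomial regression model will be replaced with a Poisson regression model". It names no scale parameter, robust variance, dispersion check or attempt to refit.

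SAP 9.6.2.2.2 carries the method over: "The analysis for 108/110 PEx Analysis Set will be similar to 106/110 PE Analysis Set", with different fixed effects. It then adds: "Similarly the number of PEx (i) requiring hospitalization, and (ii) requiring IV antibiotic therapy will be analyzed". Section 9.6.2.2.1 makes the same extension, so three counts in two sets give six models.

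Protocol 12.3.4.2 names a negative binomial model for this endpoint and mentions no Poisson fallback. By contrast, the MMRM fallback in SAP 9.6.2.1.1 is tied to a cause, the unstructured covariance. The exacerbation fallback is tied to none.

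**The concern.** A negative binomial fit can fail for reasons that call for different responses. If the estimated dispersion is close to zero, the model is close to Poisson and switching does little harm. If the optimiser fails while counts really vary more than Poisson allows, switching sets the variance equal to the mean and discards the excess. The rule treats both cases alike.

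At stake is the interval. With no between-group testing planned (SAP 9.6.2), the event rate and its 95% CI are what this model reports. An interval that is too narrow would overstate how well the long-term exacerbation rate is known.

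**Working it through.** **Inputs from the documents.** The model, offset and fallback are as described above. Enrolment is "464 subjects from Study 106" and "227 subjects from Study 108" (SAP 6.2); the exacerbation sets can differ, because they also include some parent-study subjects who did not roll over. Follow-up: "The Treatment Period will be approximately 96 weeks" (SAP 6.1), that is 96/52 ≈ 1.85 years, plus parent-study TEZ/IVA time for some subjects.

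**Not in the documents.** There is no exacerbation rate, dispersion or precision target, so there is no planned figure to reproduce. All means, rates and k values below are assumptions.

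**Formulas.** With mean count m and dispersion k:
- negative binomial variance = m(1 + km); Poisson variance = m
- Poisson SE ÷ correct SE for a log rate = 1/sqrt(1 + km)
- actual coverage of a nominal 95% CI = 2Φ(1.96/sqrt(1 + km)) − 1

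For example, m = 0.2 and k = 2 give 1 + 0.4 = 1.4 and a ratio of 1/1.183 = 0.85. Coverage is 2Φ(1.657) − 1 = 90.2%.

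| m | k | 1 + km | Width ratio | Coverage |
|---|---|---|---|---|
| any | 0 | 1 | 1.00 | 95.0% |
| 0.2 | 1 | 1.2 | 0.91 | 92.6% |
| 0.2 | 2 | 1.4 | 0.85 | 90.2% |
| 0.5 | 0.5 | 1.25 | 0.89 | 92.0% |
| 1 | 1 | 2 | 0.71 | 83.4% |
| 2 | 2 | 5 | 0.45 | 61.9% |

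A mean of 0.2 corresponds to roughly 0.1 events per year (0.1 × 1.85 = 0.185). Simulation with n = 230 and 200,000 replicates agrees with the formula: 93.2% and 90.9% for the two rows at m = 0.2, then 92.8%, 83.1% and 62.4% for the last three rows.

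**How often the fallback would run.** The table gives coverage if Poisson is used, not the chance that it is used. The second simulation used n = 464 and n = 227, 400 replicates per scenario, two equal groups with about 1.85 and 2.3 years of exposure, 30% of subjects with shortened follow-up, a log-time offset and one optimiser. Negative binomial non-convergence was:

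| Rate per year | k = 0 | k = 0.5 to 2 |
|---|---|---|
| 0.1 | 22.8–24.0% | 1.5–9.0% |
| 0.3 | 34.5–35.5% | 0–1.5% |
| 0.8 | 0.2–2.5% | 0% |

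Failure is mostly a near-zero-dispersion event. With real overdispersion it occurs mainly for rare counts.

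**What happens when it fails.** Two kinds of failure were examined.
- *Estimated dispersion at zero* (intercept-only model, n = 230, 20,000 replicates). This never occurred at m = 1, k = 1 or at m = 2, k = 2. It occurred in 4% of replicates at m = 0.5, k = 0.5, with Poisson coverage of about 91% among those. At m = 0.2, k = 2 it occurred in 2%, with coverage of about 83%. For m of 0.05 to 0.1 and k of 0.5 to 2, coverage among such replicates was about 91 to 97%. A sandwich variance gave no gain in failures of this kind.
- *Numerical failure* (covariates included, n = 227). Some optimiser-dependent failures showed clear overdispersion: Pearson scale about 1.5 to 4, and sandwich SE 1.2 to 2 times the Poisson SE. These agree, since sqrt(1.5) = 1.22 and sqrt(4) = 2.

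**The case against.** The strongest case against is that the harmful branch is rarely reached. Where overdispersion would hurt most, at higher means, the negative binomial model almost always fits. Where it tends to fail, dispersion is near zero or counts are rare, so Poisson is right or only mildly wrong. The SAP also deserves credit for fixing a fallback in advance, and it does not forbid scaling; it is silent on variance. Nothing confirmatory depends on this interval. Most of that stands and limits the size of the point. It does not remove it, because numerical failures with clear overdispersion did occur in simulation and the rule would handle them badly.

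A reader might infer three stronger things that the documents do not support:
- *That the plan's intervals would have coverage near 83% or 62%.* Those values need the fallback to be used at m = 1, k = 1 or m = 2, k = 2, where failure is unlikely.
- *That the fallback contradicts the reason for choosing the negative binomial model.* Neither document gives a reason for that choice.
- *That sparse hospitalised and IV counts make the problem worst.* Sparseness may make failure more likely, but a low mean also makes k × mean small. An empty cell is a problem of the mean model, which Poisson shares and which no variance correction repairs.

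**Conclusion.** The point holds in a conditional form. The fallback applies whatever the cause of failure and has no stated allowance for overdispersion. At zero dispersion it does no harm. If a fit fails numerically while counts are overdispersed, the 95% CI for the event rate is too narrow. In the setting where this is most plausible, sparse counts with an assumed mean near 0.2 and k of 1 to 2, the width is 0.85 to 0.91 of what it should be and coverage is about 90 to 93%.

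These sizes rest on assumed rates and dispersions, and the failure frequencies depend on the software. The consequence is limited to the interval of a secondary endpoint. It is a worthwhile refinement of minor importance.

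**What to change.** Replace the fallback sentence in SAP 9.6.2.2.1 with a two-step rule, and state that it governs all six exacerbation count models:
1. Refit the negative binomial model with other starting values or another optimiser.
2. If it still fails, fit Poisson regression with the same covariates and offset, and take the CI from a robust (sandwich) variance or from a Pearson scale factor not allowed below 1. Choose one of the two in advance and report which model was used.

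In the 400-replicate simulation, Poisson with a sandwich variance had coverage of 93.0 to 96.5% in every scenario. Plain Poisson fell to 66.2% (n = 464) and 69.8% (n = 227) at 0.8 per year and k = 2. These figures cover all replicates, not only those where the negative binomial fit failed.

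The cost is a short SAP edit and one or two program options. With no overdispersion the interval barely changes. The fix has limits: it does not repair failures caused by empty cells, and a sandwich variance can be unstable with very few events.

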9.6.2.2.2 Subjects in 108/110 PEx Analysis Set

The analysis for 108/110 PEx Analysis Set will be similar to 106/110 PE Analysis Set, with the exception of different fixed effects: treatment (TEZ/IVA, IVA-TEZ/IVA, and PBO-TEZ/IVA), residual function mutation (Class V non-canonical splice and Classes II to IV residual function), age group at screening (<18, ≥ 18 years old), and parent study baseline ppFEV₁.

Similarly the number of PEx (i) requiring hospitalization, and (ii) requiring IV antibiotic therapy will be analyzed.

9.6.2.3 Time to First Pulmonary Exacerbation

9.6.2.3.1 Subjects in 106/110 PEx Analysis Set

Time-to-first PEx on TEZ/IVA during PEx Analysis Period will be analyzed and plotted by treatment group using the Kaplan-Meier approach.

Subjects without a PEx by the end of PEx Analysis Period will be censored at the time-point corresponding to the end of PEx Analysis Period.

9.6.2.3.2 Subjects in 108/110 PEx Analysis Set

The analysis of time-to-first PEx for 108/110 PEx Analysis Set will be similar to that for 106/110 PEx Analysis Set.

9.6.2.4 Other Efficacy Endpoints

For all the other efficacy endpoints (including relative change in ppFEV₁ from baseline, absolute change in BMI from baseline, absolute change in BMI z- score from baseline, absolute change in CFQ-R Respiratory Domain Score from baseline, absolute change in weight from baseline, absolute change in weight z-score from baseline, absolute change in height z-score from baseline), the analysis will be similar to the analysis of absolute change in ppFEV₁ from baseline. Note that for CFQ-R Respiratory Domain Score, the Pooled 'Children Ages 12 and 13' Version and 'Adolescents and Adults' Version is used for MMRM based approach and descriptive summary, 'Parents/Caregivers' Version is also used for descriptive summary.

9.6.2.4.1 Subjects in 106/110 ES and 108/110 ES

The similar analysis will be performed as the analysis of absolute change in ppFEV₁ from baseline for 106/110 ES or 108/110 ES during 110 Efficacy Analysis Period. However, in the MMRM models of all other efficacy endpoints, the terms involving parent study baseline ppFEV₁ will be replaced by similar terms involving the corresponding endpoint in parent study. Similarly, the results based on MMRM along with descriptive statistics for observed values and absolute changes from baseline will be presented at scheduled visits within each treatment group, and LS means ($\pm 95\%$ CI) for absolute change from baseline at each visit will also be plotted by treatment groups.

9.6.2.4.2 Subjects in FAS Who Roll Over from Study 103 and 111

For subjects in FAS who rolled over from Study 103 and 111 respectively, descriptive summary statistics of observed values and absolute or relative changes from baseline in these efficacy endpoints will be provided at scheduled visit during 110 Efficacy Analysis Period.

9.7 Safety Analysis

9.7.1 Adverse Events

For each individual parent study, summary table of treatment emergent AEs during the respective parent study will be included in the Study 110 CSR. The parent studies are 103, 111, 106, 108, 107 and 109.

The analysis of Adverse Events in the rest of section 9.7.1 will be based on the Safety Set during **110 TE Period.**

For analysis purposes, AEs will be categorized as pre-treatment AEs, treatment-emergent adverse events (TEAEs), or post-treatment AEs:

- **Pretreatment AE:** any AE that started before the first dose of study drug in Part A.
- **TEAE:** any AE that increased in severity or that was newly developed at or after the first dose of study drug in Study Part A through the end of 110 TE Period.
- **Post-treatment AE:** any AE that increased in severity or that was newly developed after 110 TE Period.

For AEs with missing or partial start date, if there is no clear evidence that the AEs started (or increased in severity) before the first dose, the start date will be imputed to the first dosing date and the AE will be considered as TEAE. As an intermediate step for programming purposes, imputation rules for missing or partially missing AE start/end dates are defined in [Section 11.4](#).

TEAEs will be classified into 4 categories of relationship to the study drugs: not related, unlikely related, possibly related, related.

TEAEs will be classified into 4 categories of severity:

- **Mild (Grade 1):** Mild level of discomfort and does not interfere with regular activities
- **Moderate (Grade 2):** Moderate level of discomfort and significantly interferes with regular activities
- **Severe (Grade 3):** Significant level of discomfort and prevents regular activities
- **Life-threatening (Grade 4 and 5):** Any adverse drug experience that places the subject, in the view of the investigator, at immediate risk of death.

All the summary tables of TEAEs display counts and exposure-adjusted event rates for the Safety Set in Study 110.

9.7.1.1 Overview of TEAEs

An overview of all TEAEs will be summarized the following categories:

- Any TEAEs
- TEAEs by strongest relationship
- Related TEAEs
- TEAEs by maximum severity
- Grade 3/4 TEAEs
- Serious TEAEs
- Related serious TEAEs
- TEAEs leading to treatment discontinuation (this will capture TEAEs leading to discontinuation to either the morning or the evening tablets)
- TEAEs leading to treatment interruption (this will capture TEAEs leading to interruption to either the morning or the evening tablets)
- TEAE leading to death

9.7.1.2 TEAEs, Related TEAEs, Serious TEAEs, Related Serious TEAEs, Grade 3/4 TEAEs

Using MedDRA System Organ Class (SOC) and Preferred Term (PT), the number of subjects and exposure-adjusted event rates for the following TEAEs are summarized based on the Safety Set during 110 TE Period:

- TEAEs by PT and by SOC/PT

- Related TEAEs by SOC/PT
- Serious TEAEs by PT and by SOC/PT
- Related serious TEAEs by SOC/PT
- Grade 3/4 TEAEs by SOC/PT

Multiple occurrences of the same adverse event or a continuing adverse event for the same subject will be counted once. Related adverse events include related, possibly related, and missing categories. The summary tables will be presented in descending order of frequencies in the column based on Safety Set in Study 110.

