12.3.5.1 Adverse Events

For analysis purposes, AEs will be classified as pretreatment AEs, TEAEs, or post-treatment AEs.

- **Pretreatment AE:** any AE that increased in severity or newly developed before the first active dose of VX-661/ivacaftor or ivacaftor alone in the TE Period. For subjects who participate in another qualified Vertex study before completing Study VX14-661-110 assessments and re-enroll in Study VX14-661-110, pretreatment AEs include any AE that increased in severity or began before the first dose of VX-661/ivacaftor in the TE Period, and any AE that increased in severity or began after signing informed consent/assent for re-

enrollment and before the first dose of VX-661/ivacaftor after re-enrollment in Study VX14-661-110.

- **TEAE:** any AE that increased in severity or began at, or after, the first active dose of VX-661/ivacaftor or ivacaftor alone in the TE Period.
- **Post-treatment AE:** any AE that increased in severity or began beyond the TE Period.

For AEs with missing or partial start dates, if there is no clear evidence that the AEs started before or after study treatment, then the AEs will be classified as TEAEs.

An overview of AEs table will include the following.

- All TEAEs
- TEAEs by strongest relationship
- Related TEAEs
- TEAEs by maximum severity
- Grade 3/4 TEAEs
- Serious TEAEs
- Related serious TEAEs
- TEAEs leading to treatment discontinuation
- TEAEs leading to treatment interruption
- TEAEs leading to death

The following summary tables of TEAEs will also be provided:

- All TEAEs by PT and by SOC/PT
- Related TEAEs by SOC/PT
- Serious TEAEs by PT and by SOC/PT
- Related serious TEAEs by SOC/PT
- Grade 3/4 TEAEs by SOC/PT
- TEAEs leading to treatment discontinuation
- TEAEs leading to treatment interruption
- TEAEs leading to death
- Treatment-emergent elevated transaminases events by PT
- Treatment-emergent respiratory events or symptoms by PT

Summaries will be presented by MedDRA system organ class and preferred term using frequency counts and percentages (i.e., number and percentage of subjects with an event as well as total number of events). When summarizing the number and percentage of subjects with an event, subjects with multiple occurrences of the same AE or a continuing AE will be counted once, only the maximum severity level will be presented in the severity summaries, and the

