worst/highest relationship level in the relationship summaries. An AE overview table will be provided. A separate table will summarize all TEAEs when each of them is considered unique, hereafter referred to as an AE count table. In addition, a listing containing individual subject AE data for all deaths and other serious and significant AEs will be provided separately. All AEs, including pre- and post-treatment AEs, will be presented in individual subject data listings.

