9.7.1.3 TEAEs Leading to Treatment Discontinuation, Treatment Interruption, Death

The number of subjects and exposure-adjusted event rate for TEAEs leading to treatment discontinuation, TEAEs leading to treatment interruption, and TEAEs leading to death will be summarized by SOC/PT for Safety Set during 110 TE Period.

In addition, the following listings will be provided for Safety Set during 110 TE Period:

- Listing of TEAEs leading to treatment discontinuation
- Listing of TEAEs leading to treatment interruption
- Listing of AEs leading to death
- Listing of Serious AEs
- Listing of all AEs by subject
- Listing of TEAEs by preferred term

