9.7.1.4 Elevated Transaminase, Respiratory Events or Symptoms

Respiratory events (including symptoms) are defined as any of the following 7 TEAE PTs: Chest Discomfort, Dyspnoea, Respiration abnormal, Asthma, Bronchial hyperreactivity, Bronchospasm, Wheezing.

Respiratory symptoms are defined as any of the following 3 TEAE PTs: Chest Discomfort, Dyspnoea, Respiration abnormal.

Elevated transaminase is defined as the occurrence of any of the following TEAE preferred terms: Alanine aminotransferase abnormal, Alanine aminotransferase increased, Aspartate aminotransferase abnormal, Aspartate aminotransferase increased, Transaminases abnormal, Transaminases increased, Liver function test abnormal, Liver function test increased, Hypertransaminasaemia, Hepatic enzyme abnormal, Hepatic enzyme increased.

A summary of elevated transaminase, respiratory events and respiratory symptoms counts and exposure-adjusted event rate will be presented by PT for Safety Set during 110 TE Period.

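### Applied as written, the SAP 9.5 exposure formula counts re-enrolled subjects' time in another study; separately, SAP 9.7.1.2 states count-once without limiting it to subject counts, beside event rates

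*SAP*

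**What the plan says.** **Exposure.** SAP 9.5 (Study Drug Exposure and Compliance) introduces cumulative TEZ/IVA exposure as resting on the 110 TE Period. It then computes last TEZ/IVA dose date minus first TEZ/IVA dose date plus one day, disregarding any interruption in between. The compliance rate in the same section divides interrupted days by this duration. SAP 9.1 removes time in another study from the 110 TE Period for subjects who leave and re-enrol. SAP 8.1 and 8.2 remove the gap between the last dose before leaving and the first dose after return from their own periods. Protocol 12.3.3.4 has the same last-minus-first form, so the SAP appears to have inherited it.

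**Adverse events.** SAP 9.7.1 states: "All the summary tables of TEAEs display counts and exposure-adjusted event rates for the Safety Set in Study 110". In SAP 9.7.1.2, "the number of subjects and exposure-adjusted event rates for the following TEAEs are summarized based on the Safety Set during 110 TE Period", and the section then adds: "Multiple occurrences of the same adverse event or a continuing adverse event for the same subject will be counted once". The visible text does not say which column that sentence governs. Protocol 12.3.5.1 does limit its own version, which opens "When summarizing the number and percentage of subjects with an event, subjects with multiple occurrences of the same AE". It also asks for the "number and percentage of subjects with an event as well as total number of events", and adds: "A separate table will summarize all TEAEs when each of them is considered unique, hereafter referred to as an AE count table". SAP 9.7.1.3 ("The number of subjects and exposure-adjusted event rate for TEAEs leading to treatment discontinuation") and SAP 9.7.1.4 ("respiratory events and respiratory symptoms counts and exposure-adjusted event rate will be presented by PT") use the same kind of rate without a count-once sentence.

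**The concern.** On exposure, the SAP takes care to exclude off-study time from three analysis periods, but its one explicit exposure formula has no step that does so. A programmer who follows the formula would credit a re-enrolled subject with TEZ/IVA exposure while that subject was in a different trial. The same figure would then enter that subject's compliance rate.

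On adverse events, a count-once numerator over full follow-up is neither an event rate nor a proper first-event rate: later events are dropped while the time after the first event is kept. Adverse events are a main component of the primary endpoint, and the by-term tables in 9.7.1.2 are their main summary. Recurrence over 96 weeks is something a long rollover study is well placed to show. The SAP states both parts of the rate for pulmonary exacerbations (numerator in 9.6.1.2, log-duration offset in 9.6.2.2.1). The visible SAP gives neither part for adverse events.

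**Working it through.** The plan states no figure to reproduce. It gives no adverse event rate, no number re-enrolled and no length of absence. The only documentary inputs are the treatment period of about 96 weeks (SAP 6.1), the SAP 9.5 formulas and the enrolment counts in SAP 6.2. All other inputs are assumptions.

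**Part 1: SAP 9.5**

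Assume *d* = 96 dosing weeks (672 days) and an absence of *g* = 12 or 24 weeks (84 or 168 days). The formula uses calendar dates. The consecutive study-day numbering in SAP 6.1 (stop at Day 50, resume at Day 51) therefore does not remove the gap.

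- Duration from the formula = *d* + *g*: 672 + 84 = 756 days, or 672 + 168 = 840 days.
- Overstatement = *g*/*d*: 84/672 = 12.5%, or 168/672 = 25%.
- Compliance for a fully compliant subject, if the gap is recorded as an interruption = 100 × [1 − *g*/(*d* + *g*)]: 100 × (1 − 84/756) = 88.9%, or 100 × (1 − 168/840) = 80.0%.
- Compliance for a true 80%, if the gap is not so recorded: interrupted days = 0.2 × 672 = 134.4, giving 100 × (1 − 134.4/756) = 82.2%, or 100 × (1 − 134.4/840) = 84.0%.
- Pooled exposure, if a share *p* re-enrols and everyone has 96 dosing weeks, rises by *p* × *g*/*d*: 0.02 × 12/96 = 0.25% up to 0.10 × 24/96 = 2.5%. Any rate that used this duration would fall by 1 − 96/(96 + *p* × *g*), about 0.2% to 2.4%.

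The bias in compliance can go either way, depending on how the absence is recorded.

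**Part 2: count-once in SAP 9.7.1.2**

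On the Protocol reading (subject column only) the loss in the rate is 0%.

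On the literal reading, with true rate *L* per person-year and follow-up *T*, the count-once rate is (1 − exp(−*LT*))/*T*. Here *T* = 672/365.25 = 1.840 years for 96 weeks and 336/365.25 = 0.920 years for 48 weeks.

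| Assumed *L* | Count-once rate, 96 wk | Loss, 96 wk | Loss, 48 wk |
|---|---|---|---|
| 0.02 | 0.0196 | 1.8% | 0.9% |
| 0.1 | 0.0913 | 8.7% | 4.5% |
| 0.2 | 0.1673 | 16.3% | 8.7% |
| 0.5 | 0.3269 | 34.6% | 19.8% |
| 1.0 | 0.4572 | 54.3% | 34.6% |

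If rates vary between subjects (gamma, dispersion 1, assumed), the count-once rate is (1 − 1/(1 + *LT*))/*T*. For *L* = 0.1, 0.5 and 1.0 the loss is 15.5%, 47.9% and 64.8% over 96 weeks, and 8.4%, 31.5% and 47.9% over 48 weeks.

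The 48-week column matters because SAP 7.1 says that subjects from Studies 107 and 109 were discontinued early. They number 159 + 138 = 297 of 1,044 (28%), and the 96-week losses are too large for them.

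**The case against.** **On 9.5.** The same sentence ties exposure to the 110 TE Period, which excludes time in the other study. The clause on interruptions fits ordinary drug interruptions, whereas leaving for another study is called discontinuation. The intention may well be to leave the gap out. That stands, and it is why a flat statement that 9.5 exposure includes off-study time would go too far. But the formula has no step that carries out this intention, so the qualifier and the arithmetic conflict.

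**On count-once.** The Protocol reading is at least as natural. The sentence speaks of occurrences in the same subject, the first statistic named is the number of subjects, and the second is called an event rate. The SAP nowhere announces a departure from the Protocol. Dyspnoea would receive a by-term rate in both 9.7.1.2 and 9.7.1.4, and the two could disagree. They do so only if the literal reading is assumed first, so this is not independent evidence for it. All of this stands.

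**Redaction.** The SAP contents show blacked-out entries directly after 9.7.1.4 and after 11.4. A rate definition or an AE count table could be there. A reader might infer that the Protocol's table was dropped; the documents do not show that.

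**A link between the two points.** A reader might infer that inflated 9.5 exposure lowers the adverse event rates. The SAP does not say that those rates use the 9.5 duration, so that chain is not supported.

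**Conclusion.** Both points hold as separate clarifications of minor severity.

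The firmer one is SAP 9.5: taken as written, the formula conflicts with its own reference to the 110 TE Period and with SAP 9.1. Only re-enrolled subjects are affected, by 12.5% to 25% of exposure each under the assumed 12 to 24 weeks away. The pooled effect looks small (0.25% to 2.5% of exposure if 2% to 10% re-enrol) but cannot be settled from the documents.

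The second is an ambiguity. It would be tempting to conclude that the TEAE rates will be understated. The documents do not support that, because the Protocol reading loses nothing. The loss of about 9% to 54% (assumed 0.1 to 1.0 events per person-year, constant rate, 96 weeks) arises only if count-once is applied to the rate numerator over full exposure. Even then it falls mainly on common recurrent preferred terms. Rare, serious and Grade 3/4 terms would probably change little, subject counts would not change, and every occurrence remains in the by-subject listing in SAP 9.7.1.3.

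**What to change.** 1. **SAP 9.5:** for re-enrolled subjects, compute exposure as the sum of the dosing episodes in Study 110, each as last minus first dose date plus one day. Use that same duration as the compliance denominator, and state that the absence is not an interruption interval.
2. **SAP 9.7.1.2:** confine the count-once rule to the number-of-subjects column, as Protocol 12.3.5.1 does.
3. **SAP 9.7.1.1 to 9.7.1.4:** define one event rate for all these tables: all TEAE occurrences in the 110 TE Period divided by 110 TE Period person-time, excluding time in the other study, with the time unit stated. Say whether the counts shown are events or subjects.
4. Include the Protocol's AE count table. If redacted text already covers this table or the rate definition, a cross-reference is enough.

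The cost is SAP wording and table programming. No new data are needed. If the Protocol reading was always intended, items 2 and 3 simply record it.
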